## ABBREVIATIONS

[figure not shown]
CI	Chief Investigator
CO	Co-Investigator
CRF	Case Report Form
GDHCRF	Glasgow Dental Hospital Clinical Research Facility
PD	Periodontal Disease
PIL	Participant Information Leaflet
R&D	Research and Development
REC	Research Ethics Committee
SD	Standard Deviation
FM	FULL MOUTH
HS	HAND SCALE
USS	ULTRASONIC SCALER

## STUDY SYNOPSIS

Title of Study:	The Immune Response after Periodontal Treatment
Study Centre:	Glasgow Dental Hospital
Duration of Study:	36 MONTHS
Primary Objective:	To identify changes in systemic markers of inflammation following periodontal treatment, comparing two standard treatment modalities (hands scaling and ultrasonic scaling)
Secondary Objectives:	To investigate bacteraemia, composition and function of oral bacteria, treatment outcomes following periodontal treatment, patient and operator preferences, and treatment time comparing hand scaling and ultrasonic scaling.
Primary Endpoint:	C-reactive protein in the circulation following treatment.
Rationale:	To determine whether hand scaling or ultrasonic scaling are different at inducing a systemic inflammatory response.
Methodology :	RCT
Sample Size:	42 patients (TBC)
Screening:	Patients referred to Glasgow Dental Hospital Unit of Periodontics requiring periodontal treatment at Glasgow Dental Hospital.
Registration/ Randomisation:	Patients and their samples will be assigned a study code. There will be (stratified) randomisation to treatment with either hand scaling or ultrasonic scaling
Main Inclusion Criteria:	
 
• Provision of signed, written, informed consent to participate
 
• Men or women aged 18 years to 70 years inclusive
 
• Periodontal disease requiring treatment at Glasgow Dental Hospital
 

Main Exclusion Criteria:	
 
• Known or suspected high risk for tuberculosis, hepatitis B or HIV infections
 
• Require interpreter/non English language written material to understand and provide, or any other reason for being unable to provide written, informed consent
 
• History of bleeding diathesis
 
• Females using contraceptive methods.
 
• Pregnant or lactating females.
 
• Reported diagnosis of any systemic illnesses including cardiovascular, renal, and liver diseases.
 

	
 
• Any pharmacological treatment within 3 months before the beginning of periodontal treatment.
 
• Specialist Periodontal treatment in the previous 6 months.
 
• Patients who will not tolerate Ultrasonic instrumentation even with local anaesthesia.
 


Statistical Analysis:
	
Different types of data will be generated from the study, e.g.
 
 
- Serum CRP pre and post treatment.
 
- Serum cytokine levels pre and post treatment
 
- Bacteraemia pre and post treatment
 
- Composition and function of oral bacteria pre and post treatment.
 
- Clinical data to provide a measure of severity and extent of periodontal disease pre and post treatment.
 
- Patient centred outcomes of each treatment modality.
 
- See statistical analysis plan (SAP) for further details.
 

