## SCHEDULE OF ASSESSMENTS

Study Procedure	Screening initial consultant appointment	Base line	TREATMENT VISITS	DAY 1 WITHIN 24HR	Day 7 +/- 24HR	Day 90 +/- 10DAY
Study information given	Y					
Review Inclusion/Exclusion Criteria	Y	Y	Y	Y	Y	Y
Obtain initial indication if patient will consider study and appoint for combined study/first treatment visit	Y					
Obtain written consent		Y				
Randomisation		Y				
FMPS & FMBS & Periodontal charting	*	Y				
Blood Collection ( 8-10am )		y				
blood pressure and BMI record		y				
Medical History	Y	Y	Y	Y	Y	Y
OHI		y	Y		Y	Y
Sample collection (blood, plaque, GCF, saliva)		√		Y	Y	Y
Obtain^/Review consent			Y	Y	Y	Y
Complete CRF		Y	Y	Y	Y	Y

\*deepest site on each tooth recorded only

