#### **3.3 Exclusion criteria**

- Known or suspected high risk for tuberculosis, hepatitis B or HIV infections
- Require interpreter/non English language written material to understand and provide, or any other reason for being unable to provide written, informed consent
- History of bleeding diathesis
- Pregnant or lactating females.
- Reported diagnosis of any systemic illnesses including cardiovascular, renal, and liver diseases, and/or regular use of medication to control systemic illness.
- Any pharmacological treatment within 1 month before the beginning of the study, including routine use of any over the counter medications.
- Specialist Periodontal treatment in the previous 6 months.

Randomisation: patients will be stratified according to smoking status then randomized to one of two groups (hand vs ultrasonic) according to the randomization schedule (permuted blocks of size 4 and 6). The randomization schedule will be computer generated and allocation will be concealed up until the point of treatment. Masking: it will not be possible to mask the clinicians providing the treatment; however the researcher collecting the samples and undertaking the analysis will be masked to group allocation, through the use of anonymised coded samples. All other study personnel will not have access to identifiable data.

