### **3.4 Identification of participants and consent**

Patients will be identified by the CI or other clinician responsible for the patient. Patients will be screened at this time to establish eligibility. The inclusion/exclusion criteria will be evident from the information taken as part of the normal clinical procedure (eg history, examination and treatment plan). Eligible patients will be initially informed of the existence of the study and approached by the consultant or his/her representative who is treating the patient (E.g. specialist trainee/house officer/GDP/DCP). This initial contact will be to provide the patient with the Participant Information Leaflet (PIL) and establish whether they would consider taking part. At the subsequent visit, (Screening visit), the CI/CO/Registrar/consultant or research nurse will ask whether the patient would like to take part and obtain consent. At each stage, it will be made clear to the patient that that participation is voluntary and they can leave the study at any time without their care being affected.

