### **3.5 Withdrawal of subjects**

Patients will be withdrawn for the study if they are no longer eligible (e.g. due to a change in general health) or if the patient withdraws their consent to participate, or if for any other reason the CI or patient's consultant deems it detrimental to the patient to continue to participate. Withdrawal will be immediate. The CI will be informed and will confirm whether the patient wishes any previously obtained samples and associated data withdrawn from the study. The reason for withdrawal and the subsequent action taken will be documented on a case-by-case basis as an addition to the case report form (CRF).

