#### **Baseline visit:**

If the patients initially said YES to participating in the study at the screening visit, at this visit, prior to the start of treatment the patient will be asked if they have further considered participation in the study. If yes, consent for sample collection will be sought and samples will be collected by the GDHCRF research nurse and/or dentist/hygienist (the hygienist or dentist will generally only collect plaque samples as s/he will be removing the plaque anyway). This visit includes FMPS & FMBS & Periodontal charting, blood pressure recording, BMI recording and sample collection of GCF, plaque & blood). This visit is also for initial periodontal charting and initial treatment. This visit includes detailed tooth and gum home care instructions and a superficial scaling of the teeth. This is usually carried out by a staff or research hygienist, but may also be undertaken by training grade staff under the supervision of a consultant.

gingival indices will be taken. The patient will then be randomised to full mouth non-surgical periodontal treatment using either hand scalers or ultrasonic instrumentation. Appointments will be made for patient to attend for treatment visits, Day1, Day 7 and Day 90 visits with time in the GDHCRF for sample collection / blood pressure, BMI and periodontal charting where applicable.

**Treatment visits** - full mouth non-surgical periodontal treatment will be carried out within a 24hr period (+/- 18hr) either using hand instrumentation or ultrasonic instrumentation as per randomization. At the last treatment visit the clinician will verbally enquire whether the patient is happy to continue participation in the study. If yes - then the patient should attend Day 1 (24hrs later (+/- 18hrs) with time in the GDHCRF for sample collection / blood pressure recording.

**Day 1** - 24 hours (+/-18hrs) after treatment completed, further samples (GCF/Plaque/blood) and blood pressure recording will be performed. At this visit the clinician will verbally enquire whether the patient is happy to continue participation in the study. If yes - then the patient should attend Day 7 (+/- 1 day) with time in the GDHCRF for sample collection / blood pressure recording, & review of ohi

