#### ***Allocation Concealment***

Patients will be allocated to each arm of the study by a member of the research team not involved with the clinical delivery of the experimental interventions. Upon attending their treatment appointment, an opaque envelope will contain the allocated intervention arm for the patient. This will be opened immediately before treatment is commenced.

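### The two exclusion lists disagree on ultrasonic intolerance, and the withdrawal rule does not stop that criterion being used after randomisation in the ultrasonic arm only

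*Combined protocol and SAP*

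**What the plan says.** **Two lists.** The Study Synopsis (Main Exclusion Criteria) excludes "Patients who will not tolerate Ultrasonic instrumentation even with local anaesthesia". Section 3.3 does not. The synopsis also excludes women using contraception, which section 3.3 does not, and sets a 3-month medication-free window before periodontal treatment. Section 3.3 has instead "Any pharmacological treatment within 1 month before the beginning of the study". Neither place says which list takes precedence.

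**When eligibility is judged.** Section 3.4 points to entry: "The inclusion/exclusion criteria will be evident from the information taken as part of the normal clinical procedure". The Schedule of Assessments, however, marks the row "Review Inclusion/Exclusion Criteria" in all six columns, from screening through the treatment visits to Days 1, 7 and 90. Randomisation is in the baseline column.

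**What follows from ineligibility.** Section 3.5: "Patients will be withdrawn for the study if they are no longer eligible". Withdrawal takes effect at once, and no later sampling is described. The same section allows withdrawal when the Chief Investigator or the patient's consultant thinks that continuing would harm the patient.

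**When the arm is known.** The allocation envelope is used at the treatment appointment: "This will be opened immediately before treatment is commenced". Section 4.1 implies that treatment can take more than one session: "At the last treatment visit the clinician will verbally enquire whether the patient is happy to continue participation in the study".

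**The concern.** Most exclusion criteria can be judged alike in both arms at any time. Tolerance of one study instrument cannot be, once allocated treatment has begun: only ultrasonic-arm patients then receive full-mouth ultrasonic treatment and can show that they do not tolerate it. If that is treated as loss of eligibility, they leave the study while their counterparts in the hand arm stay.

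A patient withdrawn at a treatment visit gives no Day 1, Day 7 or Day 90 CRP, and so contributes nothing to the primary outcome. Analysis by randomised arm cannot restore samples that were never taken. The SAP text in section 5.1 names no analysis set and no rule for withdrawn patients. That gap is general and does not come from this criterion, but it means that nothing there protects these patients either. The direction of any bias is unknown.

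**Working it through.** **Step 1. The texts side by side**

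| Item | Study Synopsis | Sections 3.2 and 3.3 |
|---|---|---|
| Ultrasonic intolerance | excluded | not listed |
| Women using contraception | excluded | not listed |
| Medication-free window | 3 months | 1 month |
| Place of treatment | Glasgow Dental Hospital | hospital or general dental practice |

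The synopsis also marks the sample size of 42 as still to be confirmed; section 3.1 and the Sample Size text do not.

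**Step 2. The route.** A review before the first session precedes exposure and cannot differ by arm on this criterion. A review can follow ultrasonic exposure at a second treatment session, or at Day 1 or later. Withdrawal at Day 1 loses the Day 1 sample if the review comes first, and the Day 7 and Day 90 samples in any case.

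**Step 3. The plan's own figure.** Inputs from the Sample Size text: difference 3 mg/l, SD 3 mg/l, 5% level (taken as two-sided), 80% power. The t-test calculation gives 16.7, so 17 per arm (34 in total), with power 80.7%. For 20% dropout, 34/0.8 = 42.5; the plan recruits 42, or 21 per arm. The planned size is reproduced and is not in question.

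**Step 4. Possible bias, on assumed inputs.** Let k be the number of intolerant patients in each arm of 21, and D their mean CRP change minus that of the others. The documents give neither. With no true treatment effect, each complete arm has a mean shifted by (k/21) × D. Removing these patients from the ultrasonic arm alone removes its shift, so:

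size of bias = (k/21) × D

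| k | D = 1.5 mg/l | D = 3 mg/l |
|---|---|---|
| 1 | 1/21 × 1.5 = 0.07 | 1/21 × 3 = 0.14 |
| 2 | 2/21 × 1.5 = 0.14 | 2/21 × 3 = 0.29 |
| 4 | 4/21 × 1.5 = 0.29 | 4/21 × 3 = 0.57 |

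These compare with a target difference of 3 mg/l. The sign follows the sign of D.

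**Step 5. False-positive rate.** Simulation: 200,000 trials per scenario, 21 v 21, SD 3 mg/l, no true difference, pooled t-test at two-sided 5%, intolerant ultrasonic patients withdrawn.

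| k (or mean k) | D = 3, k fixed | D = 3, k random | D = 1.5, k fixed | D = 1.5, k random |
|---|---|---|---|---|
| 1 | 5.0% | 5.2% | 5.0% | 5.0% |
| 2 | 5.4% | 5.9% | 5.1% | 5.3% |
| 4 | 7.5% | 8.2% | 5.7% | 5.8% |

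**Step 6. Power for 3 mg/l.** 21 v 21: 88.5%; 21 v 19: 86.8%; 21 v 17: 84.7%. If other dropout has already left 17 v 17 (80.7%), the loss of a further 1, 2 or 4 from one arm gives 79.4%, 78.0% or 74.5%.

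**Step 7. What continued sampling achieves.** If intolerant patients respond alike in both arms, the bias is zero and the test rejects in 5.0% to 5.1% of trials when the number affected is random (below 5% when it is fixed and equal). If stopping early itself changes CRP (stopped ultrasonic patients at 0, hand counterparts at +3 mg/l), a difference of about 0.14, 0.28 and 0.58 mg/l remains at mean k of 1, 2 and 4, with rejection of 5.3%, 6.0% and 8.9%. That difference is part of the effect of the assigned treatment, stopping included, and sampling does not remove it.

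**The case against.** The strongest reply is that only a wording inconsistency is shown, and that the bias needs a chain of events that the documents do not establish.

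- **Section 3.3 is probably the intended list.** It is the dedicated criteria section, and the synopsis looks un-updated (Step 1). This is a fair inference, but no text states precedence.
- **Intolerance should be known at entry.** Section 3.4 says so in general terms, and the synopsis item reads as a forecast. The baseline visit also includes "a superficial scaling of the teeth", which may reveal some cases before allocation. This stands in part: the instrument for that scaling is not stated, no tolerance check is described, and the criterion concerns intolerance that persists under local anaesthesia.
- **Repeated review has an ordinary purpose.** It would catch new illness, medication or pregnancy in both arms, and the example of lost eligibility in section 3.5 is a change in general health. No text names instrument intolerance as a reason to withdraw, and section 11.2 distinguishes leaving the study from stopping study treatment. This stands.
- **The size is trivial for plausible numbers.** This largely stands. Only four losses, 4/21 = 19% of one arm, combined with a difference of a full SD raise the error rate noticeably, and no document supports either value.

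Two stronger readings are tempting. A reader might infer that the plan requires withdrawal of ultrasonic-intolerant patients, so that bias is to be expected. The documents do not say that: it follows only if the synopsis criterion is applied after randomisation. A reader might equally infer that the problem disappears once section 3.3 is taken to govern. It does not quite, because the clause in section 3.5 on harm to the patient could still take a patient who cannot bear the allocated instrument out of the study altogether.

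**Conclusion.** The disagreement between the lists is certain and needs correcting. Selective loss from the ultrasonic arm is possible but not shown to be likely. It requires intolerance first seen during allocated treatment, together with either use of the synopsis criterion at a later review or use of the harm clause in section 3.5.

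The size cannot be estimated from the documents. With one or two patients affected it is probably negligible: at most 0.29 mg/l of bias and 5.9% rejection for D up to 3 mg/l. The figures for four patients illustrate an unfavourable case and are not an expected consequence. All of them rest on assumed k and D, 21 per arm, SD 3 mg/l and no true difference. Severity is minor. The point is worth making because the correction costs almost nothing and protects the primary comparison.

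**What to change.** 1. **Make the synopsis match section 3.3.** Either delete the ultrasonic criterion, or keep it in both places as known intolerance, taken from the history and assessed before randomisation only. Settle the contraception item and the medication window at the same time.
2. **Add to section 3.5:** intolerance of the allocated instrument after randomisation is not a reason for withdrawal from the study. The clinician may stop or change instrument. Unless consent is withdrawn, the patient still gives Day 1, 7 and 90 samples, timed from the end of the last session received, and is analysed in the randomised arm. Withdrawal for a change in general health stays as it is.
3. **Add a CRF line** for the instrument used and the time and reason for any stop or switch.

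The cost is a few sentences in an amendment and one CRF line, with no new visits, samples or staff. The downside is that a few patients treated partly, or with the other instrument, count in the ultrasonic arm. This slightly dilutes the contrast, and the result then includes any effect of stopping early.

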## STUDY FLOW CHART

Legend for study flow chart.

Text in **BOLD** indicates a patient visit. Grey shaded boxes indicate stages of the study which fit into the patient journey. All of these would be part of the usual patient journey in the unit of Periodontics.

## SCHEDULE OF ASSESSMENTS

Study Procedure	Screening initial consultant appointment	Base line	TREATMENT VISITS	DAY 1 WITHIN 24HR	Day 7 +/- 24HR	Day 90 +/- 10DAY
Study information given	Y					
Review Inclusion/Exclusion Criteria	Y	Y	Y	Y	Y	Y
Obtain initial indication if patient will consider study and appoint for combined study/first treatment visit	Y					
Obtain written consent		Y				
Randomisation		Y				
FMPS & FMBS & Periodontal charting	*	Y				
Blood Collection ( 8-10am )		y				
blood pressure and BMI record		y				
Medical History	Y	Y	Y	Y	Y	Y
OHI		y	Y		Y	Y
Sample collection (blood, plaque, GCF, saliva)		√		Y	Y	Y
Obtain^/Review consent			Y	Y	Y	Y
Complete CRF		Y	Y	Y	Y	Y

\*deepest site on each tooth recorded only

### 1. INTRODUCTION

#### 1.1 Background

Effective root surface debridement (RSD) is essential for successful periodontal treatment. Myriad studies demonstrate that RSD may be carried out using hand or ultrasonic instruments with equal efficacy (1). Locally, effective debridement results in reduced inflammation in the gingival tissues, ultimately preserving the dentition. Systemically, RSD results in an immediate inflammatory response with elevated C-reactive protein (CRP), and cytokines (e.g. interleukin-6 and Tumor Necrosis Factor) detectable in the serum (2). This systemic inflammation may relate to systemic dissemination of bacteria from the periodontal pockets into the circulation, during instrumentation. Bacteria are detectable in serum immediately after instrumentation (3). The incidence of the bacteraemia varies considerably between different studies,

ranging from 13% of patients (4) to 43% (5) to 55% (6). These studies used different methods of instrumentation; Kinane et al used full mouth ultrasonic scale, Zhang et al used a mixture of hand and ultrasonic instruments, and Heimdahl et al used curettes only. Whilst tempting to speculate that ultrasonic instrumentation induces less bacteraemia than hand instrumentation, *there is no direct comparison of the effect of ultrasonic instrumentation with hand instrumentation on post treatment systemic inflammation.*

## **1.2 Rationale**

**. We propose that ultrasonic and hand instruments may cause different immediate systemic effects on patients.** The long-term consequences of post-RSD systemic inflammation and bacteraemia are not known. In healthy individuals it could be speculated that the systemic effects of RSD are short lived, resolve, and do not harm the patient. However, in medically compromised patients, for example with vascular disease, such perturbation to systemic homeostasis could be speculated to carry a greater potential risk to health. With an aging population and increased tooth retention, more medically compromised patients receive periodontal treatment. We propose a study to investigate the systemic impact of different debridement methods, outlined in the diagram below.

## **1.3 Prior experience of periodontal research**

The Chief Investigator (CI) is a specialist periodontist treating patients with advanced and aggressive forms of periodontal disease. The CI has a developing track record in periodontal research, with current research funding in the region of £1.3 million and a number of peer reviewed publications as detailed on attached CV. The CI works in close collaboration with world-renowned immunologists and microbiologists and several consultant periodontist colleagues at the Glasgow Dental Hospital.

[name] is an extremely experienced Dental Hygienist who also has experience of dental research, including commercial and non-commercial studies, which have included treatment of periodontitis.

## **1.4 Study hypothesis**

There is a difference in the systemic response to periodontal treatment using either hand instruments, as compared with periodontal treatment using ultrasonic instruments.

## **2. STUDY OBJECTIVES**

1. To investigate systemic markers of inflammation following periodontal treatment, comparing two standard treatment modalities (hands scaling and ultrasonic scaling).
2. To investigate bacteremia, composition and function of oral bacteria, treatment outcomes following periodontal treatment, patient and operator preferences, and treatment time comparing hand scaling and ultrasonic scaling.

### **3. STUDY DESIGN**

This Randomized Controlled Trial will be performed according to the Research Governance Framework for Health and Community Care (Second edition, February 2006).

